# Feasibility testing: Pilot RCT (patient component)

After SweetMama is modified based the usability testing phase and provider feedback, which we anticipate will take 1-2 months, feasibility testing will occur with up to 50 eligible pregnant women via field testing. The goals of this phase are to field test recruitment, retention, and assessment strategies, as well as delivery of SweetMama within a pilot RCT, to assess feasibility and inform the design of a full trial assessing behavior, glycemic control, and perinatal outcomes. We will collect feasibility data regarding recruitment, technical challenges, quality assurance, and retention, as well as clinical outcomes data and patient-reported outcomes.

Women will be recruited to participate in the same manner as described above, via routine clinical interactions. Medical records will be reviewed for eligibility and women with diabetes will then be approached for verbal in-person screening and recruitment using a recruitment script (Appendix E). Participants will sign written informed consent. Enrolled women will be provided a "SweetMama timeline" document that explains the study activities, provides contact information, and outlines how to contact the team for technical help or any other needs. We will then randomized participants. Randomization, via REDCap, 76 will be unbalanced to

offer greater odds of receiving the experimental treatment in order to enhance the research team's experience with SweetMama and incentivize participation, with a target sample of 40 (randomized 1:3, stratified by DM type). The target sample size is 40, but up to 50 women may be enrolled in order to account for drop-out or the requirements of the randomization schema.

Women who are randomized to usual care will receive no orientation to or enrollment in SweetMama. They will receive surveys at enrollment, during the delivery hospitalization, and at the postpartum visit (see details in table below). Women who receive usual care will not undergo interviews.

Women who are randomized to SweetMama testing will be oriented to SweetMama use on their own Apple or Android-based phones. Once enrolled, with the support of trained research staff, participants will undergo standardized orientation to SweetMama using the introductory video developed in the usability phase. The SweetMama introductory video will be updated between the usability and feasibility testing phases. The training of the research team to perform standardized orientation and support enhances the fidelity of the intervention. Women will then use SweetMama throughout pregnancy. The curriculum delivery will be performed as described above and will be automated based on entry gestational age. Their appointment reminders will be entered into the researcher dashboard prior to appointments, and their goal messages will be set via involvement of the clinical team at appointments as recommended by the APN. If a woman starts her participation already on insulin, she will receive the supplementary insulin curriculum from enrollment; if she initiates insulin after enrollment, she will initiate the insulin curriculum that week. SweetMama users will undergo every 2-week check-ins for technical and quality assurance; these brief check-ins will take place via text, phone, email, or in-person, depending on participant preference. Use of SweetMama will continue until the completion of the postpartum visit, with a curriculum that extends through postpartum week 8. They will receive surveys at enrollment, during the delivery hospitalization, and at the postpartum visit (see details in table below). SweetMama participants will also undergo a brief 2-part exit interview (see below) focusing on feedback for SweetMama use, areas for improvement and how SweetMama affected their engagement. The primary interview will take place during the delivery hospitalization or shortly thereafter if not feasible at the time; a brief follow-up interview focusing on the postpartum curriculum will occur at the postpartum visit.

The primary outcomes of Aim 2 are feasibility (≥80% retention; see below) and satisfaction (USE, SUS, interviews). Secondary outcomes are behavioral (DES-SF, PAM, adherence), clinical (hypertensive disorders, delivery mode, birthweight, neonatal hypoglycemia, NICU admission), and glycemic control outcomes. Glycemic control will be assessed as hemoglobin A1c (final and difference from enrollment to delivery) and as proportion of blood glucose measures out of goal. Adherence will be assessed as proportion of prenatal visits attended and with available glucose data.

In order to assess these outcomes, the measures in the following table will be collected via the medical record, user interaction reports, and patient report:

All women		Additional data gathered in SweetMama arm	
Baseline	
 
Demographics, clinical data, eHEALS, NVS, DES- SF, PAM, technology comfort questionnaire
 
		
Monthly	
 
Retention (continuation in care and the study protocol)
 
	
 
SweetMama retention and adoption
 
SweetMama functionality, quality assurance & content feedback (technical check-ins)
 
	
Delivery	
 
Retention (continuation in care and the study protocol)
 
	
 
SweetMama functionality, quality assurance, & content feedback
 
Exit interview- feasibility, improvement, and engagement
 
	

	Treatment adherence		•	Satisfaction and usability: USE and SUS
	•	Behavioral measures: DES-SF, PAM	•	User interaction data (see Aim 1)
	•	Maternal and neonatal clinical data		
Postpartum	•	Behavioral measures: DES-SF, PAM	
 
Exit interview part 2 – postpartum curriculum - feasibility,
 
	
				improvement, and engagement

As in the usability testing phase, we will collect baseline information on (see details above):

- Demographic and clinical characteristics
- Electronic health literacy measured the eHealth Literacy Scale (eHEALS)65
- Health literacy measured via the Newest Vital Sign
- Diabetes self-efficacy measured via the Diabetes Empowerment Scale–Short Form (DES-SF
- Patient activation measured via the Patient Activation Measure (PAM)
- Technology comfort Using a modified version of the Technology Comfort Questionnaire (12 items), we will ask about smartphone familiarity and comfort.

We will also collect data from study and medical record upon completion on:

- Retention, measured as continuation in the study protocol
- Treatment adherence, measured as 1) retention in clinical care with completion of all recommended selfcare measures (visits attended and with glucose data available), and 2) proportion of glucose values out of range when presenting to care
- Maternal and neonatal outcomes, including glycemic control (Appendix A)

For the SweetMama arm, we will collect unique data on:

- Quality assurance and technical functioning: At each technical check-in point, we will complete a short standardized check-in regarding any errors, technical problems, or content clarifications. In this field testing phase, the 2-item quality assurance check-in will be completed by completion of a brief mobile REDCap survey.
- Interview Semi-structured interview framed by the Health Belief Model on experiences with SweetMama. Information will be designed to elicit feedback about technical problems, ease of use, satisfaction abd overall usefulness for various components of SweetMama (see Appendix F)
- Satisfaction measured via the System Usability Scale (SUS).
- Satisfaction and usability measured via the Usefulness, Satisfaction and Ease of Use (USE)
   Questionnaire
- User interaction data client event data will be identical to data in the usability phase.

[figure not shown]
As in the usability phase, only data related to how and when SweetMama is used will be collected and the format in which it is stored will contain no identifying information about users. Furthermore, the information saved on the server will only be accessible to people provided with the proper credentials (members of the research team, research collaborators, and the users themselves). All study activities will take place within Northwestern Medicine, specifically in the PAC clinic, General Obstetrics/Gynecology practice, and Maternal-Fetal Medicine practice. No physical procedures will be performed and there are no specific procedures used to monitor participants for safety or minimize risks, as this poses no more than minimal risk to participants. Source records for the study include interviews, surveys, and chart data, as described above. All questionnaires will be collected using REDCap. The study has been updated in clinicaltrials.gov per requirements.

# Feasibility testing: Pilot RCT (clinician phase)

Clinicians will be recruited using similar processes as described above for the clinician focus group phase. These stakeholders (nurses, physicians, nurse practitioners) will be individuals who care for enrollees in the pilot randomized trial, including both those who are SweetMama users and those receiving usual care. Providers will not be asked any personal questions about themselves. There will be three brief phases of provider enrollment:

- Upon patient participant enrollment, their primary provider will undergo a brief REDCap-based survey regarding perceptions of patient engagement in general, using an adapted version of the Clinician Support for Patient Activation (CSPAM) measure. The 14-item CSPAM addresses how far clinicians value people's role in the care process and indicates clinician level of endorsement about the importance of patient activation. This measure assesses a stable characteristic about a provider and thus will only be asked once. Additional questions will address their expectations for SweetMama involvement. At this point, the provider will also be provided brief education about SweetMama's goals and their involvement in the goal-setting component.
- Upon patient participant completion, providers will undergo a brief follow-up survey regarding their individual patient's engagement and adherence. Questions will be modified from the CSPAM and additional items will specifically query their opinions about SweetMama. Providers will complete this brief survey for each participant.
- Upon patient participant completion, providers will be asked to undergo a single in-depth interview.
   The qualitative interview will address if and how SweetMama affected provider roles, whether and how providers perceived benefit, and future suggestions. If a provider cared for multiple patients who used SweetMama, she will be asked to reflect on each individual participant's engagement as well as overall perspectives on the program.

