# **STUDY TIMELINES:**

Focus groups and individual user interviews: Women recruited to the focus groups and individual user interviews will have approximately 1 hour of study participation in which they will be asked to provide feedback about SweetMama while testing it and discussing its potential use during pregnancy. They will not be followed longitudinally.

Longitudinal individual testing: Women recruited to the longitudinal usability testing phase of SweetMama will actively participate for two weeks, during which time they will have frequent contact with the study team. After this period of active use, we will request patient permission to follow up their pregnancy outcomes via record review, but we will not require further information nor study participation.

Provider testing: Health care providers recruited to a focus group or individual interview will have approximately 1 hour of study participation in which they will be asked to provide feedback about SweetMama while testing it and discussing its potential clinical use. Participation in the study will be over at the end of the focus group or interview.

Pilot RCT: Women recruited to the pilot RCT phase of SweetMama will enroll in the study upon initiation of prenatal care for diabetes, which could be early in pregnancy at the time of first prenatal visit, or at a later point if they have transferred care to this site. Women will actively participate for the duration of their pregnancy and postpartum period, which could be as long as 44 weeks (for example, of a woman enrolled at 6 weeks, delivered at 40 weeks, and continued through 10 weeks), or could be as few as 20 weeks (if enrolled at

30 weeks and delivered at 40 weeks). We will follow their patient-reported and medical record outcomes throughout this time period. We will not require further information or study participation after the postpartum exit interview. Health care providers who participate in the provider survey will complete a one-time survey at the time of their patients' enrollment and another survey upon exit; the exit survey will be repeated for each patient they have who is enrolled in the pilot trial. Healthcare providers will additionally complete a one-time in-depth interview after they have had enrolled patients complete their participation.

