This message curriculum library serves as the foundation for SweetMama. This functionality has been designed to be scalable by intentionally building the capacity to pre-program the messaging library at the start of participant enrollment based on a gestational age-specific algorithm.

SweetMama includes several other patient- and theory-driven components, including:

- Favorites: All messages will be retained in an archive organized by type and chronology. Participants will be also able to "favorite" preferred messages for later review.
- Library: The library will contain dynamic content, such as storage of the messages received, as well as static content, which will contain didactic information that will always be available to participants. This will include recommended recipes, handouts, and worksheets provided by the Health Learning Center, and other tips/advice for participants.

- Goal-setting: Consistent with the Theory of Self-Efficacy, SweetMama includes individualized goal-setting
  activities. At each appointment, participants select a goal for the subsequent week with the clinical team;
  goals may be behavioral, nutritional, or other DM-related patient-driven goals. The goal will be entered
  into the SweetMama provider platform to be delivered as a patient reminder 4 days later. Goals can be
  modified and customized as needed, and goals can be delivered up to once a week. This individualized
  message's dynamic response option will ask participants whether they have accomplished the stated goal.
  A goal achievement log that encourages self-regulation behaviors will be maintained.
- Technical support: Participants will have access to "in-app" participant-initiated support. The technical support page includes instructions to call the clinic or hospital for clinical questions.
- Appointment reminders: The home page contains the time of the next appointment, and participants receive appointment reminders as messages prior to the scheduled appointment.
- Information: The home page will also provide clinic contact information, names of clinical care team, and basic information about the purpose of SweetMama.
- Introductory video: A brief orientation video will display upon first interaction with SweetMama. This video has been created to demonstrate SweetMama's features in a concise and user-friendly manner; it additionally ensures standardization of the orientation process.

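### Provider briefing on SweetMama goal-setting, and the SweetMama opinion items at exit, are not limited to the SweetMama arm, which creates an avoidable contamination risk of unknown size and mixes users with non-users

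*Combined protocol and SAP*

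**What the plan says.** The relevant text is in the current protocol, the version that adds the pilot RCT.

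- **Who the providers are.** Feasibility testing: Pilot RCT (clinician phase) recruits clinicians caring for trial enrollees, "including both those who are SweetMama users and those receiving usual care".
- **Entry step.** "Upon patient participant enrollment, their primary provider will undergo a brief REDCap-based survey regarding perceptions of patient engagement in general". The same step asks what the provider expects of SweetMama and then adds: "At this point, the provider will also be provided brief education about SweetMama's goals and their involvement in the goal-setting component". No arm condition is attached.
- **Exit step.** The follow-up survey covers the individual patient's engagement and adherence, and "additional items will specifically query their opinions about SweetMama. Providers will complete this brief survey for each participant". Study Timelines agrees: "the exit survey will be repeated for each patient they have who is enrolled in the pilot trial".
- **What goal-setting is.** Procedures lists it among the theory-driven components of SweetMama: "At each appointment, participants select a goal for the subsequent week with the clinical team". The patient component repeats that goal messages in the SweetMama arm are set with the clinical team's involvement.
- **Protection of the control arm.** The patient component states: "Women who are randomized to usual care will receive no orientation to or enrollment in SweetMama". This concerns the woman. Nothing comparable is said about her provider.
- **Analysis.** Provider surveys are to be described, with no split by the patient's arm. Retention, behavioral measures and clinical outcomes are to be compared between groups.

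**The concern.** The stated objective is a pilot RCT of SweetMama against standard of care. Most of SweetMama reaches a woman only through her phone, but choosing a goal is done face to face with the clinical team. It is the one component that a briefed clinician could carry to a woman without the app. If the briefing follows enrollment in either arm, the trial itself creates a route from the intervention to the comparator.

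The outcomes exposed are the secondary between-arm comparisons. DES-SF measures diabetes self-efficacy, the construct that goal-setting is meant to support; PAM and adherence are also compared between arms. The pilot is meant to inform a full trial, so an altered control arm that nobody measured would carry forward into that design.

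The second issue concerns the data and needs no assumption about contamination. Provider perspectives on SweetMama are a secondary aim. Opinions recorded after caring for a woman who never had the tool differ in kind from those recorded after caring for a user, and the plan does not separate them.

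**Working it through.** The plan gives no contamination rate, effect size or power figure for the pilot, so it has no figure of its own to reproduce. The check is a reading of the text plus arithmetic on the stated sample and allocation.

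**1. Is the briefing tied to arm?** The entry step is triggered by a patient's enrollment, and the providers covered include those of usual-care women. In the patient component, randomization comes after consent and enrollment, so a briefing given on enrollment could precede knowledge of the arm. Where the clinician phase means SweetMama users only, it says so: the interview asks for patient-by-patient reflection from providers whose patients used SweetMama. The briefing and the two surveys carry no such limit.

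**2. Share of exit surveys about non-users.** Inputs (patient component): target 40 women, randomized 1:3. Usual care = 40 × 1/4 = 10; SweetMama = 30. Share = 10/40 = 25% if every survey is completed. At the maximum of 50 the expected split is 12.5 and 37.5, and the share is again 25%.

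**3. How much exposure would occur anyway?** Suppose a usual-care woman's provider has m trial women in all, unrelated to arm, with a 10/30 split. The chance that at least one of the other m − 1 is a SweetMama user is 1 − C(9, m−1)/C(39, m−1):

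| m (assumed) | Calculation | Probability |
|---|---|---|
| 1 | 1 − 1 | 0 |
| 2 | 1 − 9/39 | 0.77 |
| 3 | 1 − 36/741 | 0.95 |
| 4 | 1 − 84/9139 | 0.99 |

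The documents do not give m. Procedures allows up to 30 providers. If each woman has one participating primary provider, 40/30 = 1.33 women per provider is a lower bound on the average, because 30 is a cap. The range above therefore cannot be narrowed.

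**4. What dilution would do (illustration only).** With 10 against 30 and two-sided 0.05, the standardized difference detectable with 80% power is (1.960 + 0.842) × √(1/10 + 1/30) = 1.02 SD. If contamination removed a fraction c of that difference:

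| c (assumed) | Remaining difference (SD) | Power |
|---|---|---|
| 0 | 1.02 | 80% |
| 10% | 0.92 | 71% |
| 20% | 0.82 | 61% |
| 30% | 0.72 | 50% |
| 50% | 0.51 | 29% |

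The values of c are assumptions. The table shows sensitivity and does not predict what will happen.

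**The case against.** The strongest reply is that little can actually cross. Goal-setting is part of SweetMama, from which usual-care women are excluded. The goal is entered in the SweetMama platform, comes back as a reminder, is answered in the app and is logged there; none of this reaches a woman without an account. That is right, and it limits the risk to the conversation in clinic. It does not remove the risk, because the exclusion of controls says nothing about what a briefed provider does.

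A reader might infer that usual care here is no longer standard care, or that the arm difference will be pulled toward zero. The documents support neither. They do not say whether routine diabetes visits already include goal-setting, and they give no rate of crossover. Dilution is the expected direction if crossover occurs; its occurrence and size are unknown.

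A reader might also take 1.33 women per provider as a count and conclude that most of the exposure comes from the clinician-phase rule. That needs m close to 1, which the documents do not establish. Recruitment is mainly from one low-volume clinic, and with two or three trial women per provider most control women's clinicians would be briefed anyway because of another patient. The provider focus groups planned before the pilot may also have introduced some of the same clinicians to the tool.

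The stakes are modest too. The primary outcomes are retention against an 80% target and satisfaction, with USE and SUS collected only in the SweetMama arm, and the pilot is not designed to assess clinical outcomes. Finally, each exit survey relates to one patient, so it could be reported by arm without redesign. All of this stands and limits the weight of the point. It does not explain why the briefing and the SweetMama items should follow the enrollment of a control.

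**Conclusion.** The point holds as a low-cost improvement. As written, the clinician phase briefs the primary providers of usual-care women on SweetMama's goals and on their own goal-setting role, and asks for opinions of SweetMama at exit for every participant.

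Two consequences follow, of different certainty. The mixing of provider data comes directly from the wording: about 10 of 40 exit surveys (25%), assuming the target sample, exact 1:3 allocation and full completion. The contamination is a risk of unknown size, confined to in-clinic goal-setting, and bears mainly on the between-arm comparisons of DES-SF, PAM and adherence. The primary outcomes are largely unaffected. How much of the exposure is due to this rule alone, beyond shared providers and the earlier focus groups, cannot be derived without the number of women per provider.

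**What to change.** Amend the clinician phase as follows.

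1. **Entry.** Keep the one-time CSPAM survey at a provider's first enrollee in either arm. Give the SweetMama briefing and the expectation items only after that provider's first SweetMama-arm patient has been randomized.
2. **Exit.** Show the SweetMama opinion items only for SweetMama-arm patients. Keep the engagement and adherence items for both arms, and report the survey by the patient's arm.
3. **Measurement.** Add one item to the per-patient exit survey, in both arms, asking whether goals were set with that patient at visits, and report the usual-care answers as crossover. Chart review would be less reliable: SweetMama goals are entered in its own platform, and the chart-review list in Appendix A has no goal item.

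The cost is branching in the existing REDCap survey, a sentence or two in the provider procedure, and one new item. Sample size, randomization and patient visits do not change. A provider whose first enrollee is a control (about 10/40 = 25% of first enrollees) would need a second short contact if a SweetMama-arm patient follows. The new item is the provider's own report, made with knowledge of the arm, and should be read with that in mind. Providers who see both arms will still carry some exposure, so contamination is reduced and measured, not removed.
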